9.6.3 Brief Pain Inventory – Short Form

The BPI (94) is a 9 item self-report questionnaire used to evaluate the severity of a patient's pain and the impact of this pain on the patient's daily functioning. The patient is asked to rate their worst, least, average, and current pain intensity, list current treatments and their perceived effectiveness, and rate the degree that pain interferes with general activity, mood, walking ability, normal work, relations with other persons, sleep, and enjoyment of life on a 10 point scale. The BPI will be used at screening to screen for the presence or absence of chronic pain. Additionally, BPI "pain right now" VAS will be asked at beginning of each session. This score must be 0 for patients with NO PAIN or the session will be rescheduled. PAIN group persons must report similar levels of pain each session (i.e., the BPI "pain right now" score at session 2 must be +/-20% of the "pain right now" score at session 1; PAIN group persons cannot have a "pain right now" score of 0) or the session will be rescheduled.

9.6.4 Pain Assessments

Pain will be assessed using the miscellaneous pain questionnaire from the National Health and Nutrition Examination Survey (NHANES; (83)) and the Widespread Pain Index.

9.6.5 Insomnia Assessment

The Insomnia Severity Index is a brief validated instrument that measures nighttime and daytime aspects of insomnia (84). Scores 15+ indicate clinical insomnia that is at least moderate in severity. Persons found to have clinical insomnia will be referred for further evaluation and possible treatment by their primary care provider and/or their methadone maintenance medical team.

9.7 Psychiatric Assessments

The Mini International Neuropsychiatric Interview will be conducted by [name] during screening to rule out persons with suicidal ideation or psychosis. In addition, the following scales will also be measured at Session 1: PHQ-15 (3) which provides a measure of somatization), PHQ-9 (4) which measures depressive symptoms, and GAD-7 (5) which measures anxiety symptoms.

10 EVALUATIONS BY VISIT

10.1 Visit 1 (Screening)

- 1. Review the study with the subject and obtain written informed consent and HIPAA authorization
- Assign the subject a unique screening number
- 3. Collect urine for urine drug screen (and pregnancy test if female)
- 4. Collect ROI for opioid treatment program
- Record demographics data
- 6. Record medical history
- Record drug use history
- Record concomitant medications

Version #: 1.9 Version Date: 12/09/2020 Page 19 of 37

- 9. Perform a complete physical examination
- 10. Perform and record vital signs
- 11. Perform and record oximetry
- Perform and record EKG
- 13. Perform and record MINI
- 14. Perform and record BPI
- 15. Perform and record NHANES Miscellaneous Pain Questionnaire
- 16. Perform and record Widespread Pain Index
- 17. Perform and record BPI
- 18. Schedule subject for Visit 2 (Session 1) as appropriate.
- 19. Randomize subject

10.2 Visits 2-3 (Sessions 1-2)

- 1. Record any Adverse Experiences
- Concomitant medications review
- 3. Collect Urine for UDS (and pregnancy test if female)
- Perform and record "pain right now" VAS from BPI
- 5. Record time of methadone dosing (confirm by reviewing Methasoft EHR)
- 6. Perform and record baseline values of
 - a. Vital signs
 - b. Oximetry
 - c. Pupilometer
 - d. COWS
 - e. SOWS
 - f. Pain VAS
- 7. If smoker, allow participant to smoke 20 minutes prior to study drug administration
- 8. Administer IM study drug. Record on progress note.
- 9. For every 15 minutes until two hours after IM injection, measure
 - a. Vital signs
 - b. Oximetry
 - c. Pupilometer
 - d. COWS
 - e. SOWS
 - f. Pain VAS
 - g. Subjective drug effect VASs

Version #: 1.9 Version Date: 12/09/2020 Page 20 of 37

- 10. 30 minutes after study drug administration, perform and record delay discounting task
- Perform and record PCS
- 12. Perform and record PHQ-15
- 13. Perform and record GAD-7
- 14. Perform and record PHQ-9
- 15. Perform and record Barratt Impulsivity Scale-11
- 16. Perform and record Eysenck Impulsivity Questionnaire
- 17. Perform and record Sensation Seeking Scale
- 18. Perform and record Zimbardo Time Perspective Inventory
- 19. Perform and record Insomnia Severity Index

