| CONCOMMITANT | Beyond their methadone maintenance dose, participants will be |
| MEDICATIONS | allowed to take OTC or prescription strength non-opioid analgesic |
| | medications such as acetaminophen or ibuprofen for pain throughout |
| | the study, consistent with standards of care. |
| | Prohibited : Opioid analgesics other than methadone |
| | - I |

Version #: 1.9 Version Date: 12/09/2020 Page 6 of 37

| EVALUATIONS | | |
|-----------------------|--|--|
| PRIMARY ENDPOINT | Delay discounting of money rate (k) | |
| SECONDARY | Pain VAS ratings (0-100) | |
| ENDPOINTS | Peak COWS | |
| | Peak SOWS | |
| | Peak Change from Baseline Pupil Diameter | |
| | Peak VAS of Subjective drug effects (0-100) | |
| | Drug Effects | |
| | Good Effects | |
| | Bad Effects | |
| | Liking | |
| | • Sick | |
| OTHER | Pain Catastrophizing Scale | |
| EVALUATIONS | Barratt Impulsivity Scale-11 | |
| | Eysenck Impulsivity Questionnaire | |
| | Sensation Seeking Scale | |
| | Zimbardo Time Perspective Inventory | |
| SAFETY | Incidence of adverse events | |
| EVALUATIONS | Change in vital signs from baseline (HR, BP, RR, % oxygen) | |
| | saturation) | |
| PLANNED INTERIM | When approximately 10 patients have completed the study, an interim | |
| ANALYSES | analysis will be conducted by the study statistician. If there is no trend | |
| | of differences in delay discounting between placebo and naloxone | |
| | administration sessions, we would discuss with our NIDA program | |
| | official and independent medical monitor on the following two | |
| | options: increasing the dose of naloxone to 0.15 mg or administering | |
| | 0.1 mg naloxone at trough instead of peak methadone levels. Serious adverse events will be monitored by the medical monitor throughout | |
| | the duration of the study. | |
| STATISTICS | Using methods developed by co-I [name], nonlinear regression will | |
| Primary Analysis Plan | be used to calculate individual values of k, larger k values indicate | |
| Timary Analysis I lan | greater discounting or more impulsiveness. K values are normalized | |
| | using log transformation for parametric analysis. We will use repeated | |
| | measures analyses implemented in SAS PROC MIXED. The | |
| | dependent variable is k (discounting). Independent variables include | |
| | Group (PAIN vs. NO PAIN), a fixed, between-subjects effect and | |
| | Condition (control vs. withdrawal), a repeated, within-subjects effect. | |

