4 STUDY DESIGN

4.1 Study Overview

This is an outpatient Phase 1 clinical trial investigating the effect of naloxone precipitated withdrawal on delay discounting. Eligible participants will undergo two experimental sessions presented in random order. One session will involve the measurement of delay discounting 30 minutes after double-blind intramuscular (IM) administration of placebo (normal saline) and the other will have the exact same procedures performed after double-blind IM administration of naloxone (0.1 mg). Injections will occur 2 hours after methadone dosing (peak levels). Study sessions will last 2 hours and involve pain and opioid withdrawal measures assessed at baseline and 15-minute intervals after injections. Sessions will occur at least 48 hours apart.

This is a two-year grant proposal. The first two months will be used for study start-up, the next 20 months for study recruitment and completion of all study visits, and the last two months for data analysis and manuscript preparation. Each participant is expected to participate for 2-4 weeks, depending on scheduling of two sessions.

There are three sites on the campus of Zuckerberg San Francisco General Hospital where activities will take place. (1) Opiate Treatment Outpatient Program (OTOP). Participant recruitment, data collection and storage, and some study visits will take place at OTOP. (2) Unit 5B in Building 5. ECGs during screening and unblinded study medication preparation. (3) Ward 84 in Building 80. Some study sessions may take place at Ward 84. Johns Hopkins University's Behavioral Pharmacology Research Unit (BPRU) will be the site of data analysis. Johns Hopkins will only have access to de-identified human subject data, and so a central IRB is not needed for this study.

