5.3 Safety Evaluations

- Incidence of adverse events
- Change in vital signs from baseline

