8.4.3 Administration Instructions

Prior to session commencing, participants must give a UDS that is positive for methadone and negative for illicit substances and other prescription opioids. In addition, the participant must not have any signs of intoxication and meet pain parameters described in the inclusion / exclusion criteria. During the COVID-19 pandemic, participants must also screen negative per hospital policy to be allowed into Ward 95 to begin study sessions. Lastly, the participant will smoke 1 cigarette 20 minutes prior to injection. [name] or another qualified and licensed medical clinician will administer the IM injection in the deltoid muscle of the participant. The injection will occur two hours after their daily methadone dose was given.

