9.1.5 Vital Signs

Blood pressure, pulse and respirations will be performed after resting for 5 minutes at Screening and at beginning of each session. During sessions, blood pressure, pulse and respirations will be measured every 15 minutes up until two hours after IM injection of study medication.

Version #: 1.9 Version Date: 12/09/2020 Page 16 of 37

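### The session baseline is listed before the pre-injection cigarette with no fixed time to injection; this blurs within-session change scores but does not bias the naloxone-placebo comparison

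*Combined protocol and SAP*

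**What the plan says.** Section 10.2 sets out each session as a numbered list. Step 6 is "Perform and record baseline values of" vital signs, oximetry, pupil diameter, COWS, SOWS and pain VAS. Step 7 reads "If smoker, allow participant to smoke 20 minutes prior to study drug administration". Step 8 is the injection. Section 8.4.3 also makes the cigarette the last pre-injection step, but words it for everyone: "Lastly, the participant will smoke 1 cigarette 20 minutes prior to injection".

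Section 9.1.5 says that blood pressure, pulse and respirations "will be performed after resting for 5 minutes at Screening and at beginning of each session". Sections 9.1.6 (oximetry) and 9.3 (pupil) refer only to a baseline, with no time attached.

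Two reported quantities are changes from that baseline: the secondary endpoint "Peak Change from Baseline Pupil Diameter" in the synopsis and the safety evaluation "Change in vital signs from baseline" in section 5.3.

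On session timing, section 8.4.3 states: "The injection will occur two hours after their daily methadone dose was given". Section 4.1 describes that time as peak methadone level. The synopsis gives about four hours per session and has the product given at the start of the session. Section 4.1 gives sessions of 2 hours.

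Section 9.5 has the subjective drug-effect VASs collected at baseline. Step 6 of section 10.2 omits them, and they first appear in the post-injection list at step 9.

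**The concern.** A change from baseline is normally read as what happened after study drug. Here a cigarette (for smokers at least) and some part of the approach to peak methadone level may fall between the baseline and the injection. Either could move pulse, blood pressure or pupil without any naloxone.

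Three things are at stake. First, the change reported for each study medication would include those earlier movements. Second, if the gap differs between a participant's two sessions, the paired comparison becomes noisier. The pupil matters here because section 9.3 calls it one of the most sensitive measures of withdrawal. Third, if the PAIN and NO PAIN groups differ in smoking, a comparison of the groups within one session could pick up that difference.

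**Working it through.** **1. The gap.** Post-injection measures run for 120 minutes (sections 9.1.5, 9.1.6, 9.3). Time available before injection = session length − 120 minutes.

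- Four-hour session (synopsis): 240 − 120 = 120 minutes. This equals the methadone-to-injection interval, so it corresponds to a session that starts at dosing.
- Two-hour session (section 4.1): 120 − 120 = 0 minutes. This leaves no room within the session for a cigarette 20 minutes before injection.
- Listed order in section 10.2: baseline comes before the cigarette, so the gap is at least about 20 minutes.

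The possible range is therefore about 20 to 120 minutes, a spread of 120 − 20 = 100 minutes. The upper end holds only on the four-hour reading.

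**2. The naloxone-placebo difference.** For one session, let peak change = max(post-injection readings) − B, where B is the baseline. Then

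E[naloxone change] − E[placebo change] = {E[max, naloxone] − E[max, placebo]} − {E[B, naloxone session] − E[B, placebo session]}.

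B is measured before the injection, the sessions are blinded and in random order, and procedures are the same (section 4.1). The second bracket is therefore zero wherever B is placed. Equivalently, a common shift c between baseline and injection gives max(x + c) = max(x) + c, and c cancels on subtraction.

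**3. Simulation.** The documents give no variances or nicotine or methadone effects, so these inputs are assumptions: 100 participants, eight readings at 15 to 120 minutes, a naloxone effect peaking at 1.0 unit, and reading noise with SD 0.3. The shift is drawn independently in each session with the mean and SD shown.

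| Mean shift | Shift SD | Naloxone change | Placebo change | Difference | SD of paired difference |
|---|---|---|---|---|---|
| 0 | 0 | 1.20 | 0.43 | 0.775 | 0.51 |
| −0.5 | 0 | 0.70 | −0.07 | 0.774 | 0.51 |
| +0.5 | 0 | 1.70 | 0.93 | 0.776 | 0.51 |
| −0.5 | 0.25 | 0.70 | −0.07 | 0.776 | 0.62 |
| −0.5 | 0.5 | 0.70 | −0.07 | 0.776 | 0.87 |
| −1.0 | 0.5 | 0.20 | −0.58 | 0.778 | 0.87 |

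The first row has no shift, which a baseline taken just before injection would approximate. Its placebo value of 0.43 arises because the largest of eight noisy readings is taken. Each session's mean change moves one-for-one with the shift, while the difference stays at about 0.775.

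**4. The variance cost.** With independent session shifts of SD s, SD of the paired difference = √(0.51² + 2s²).

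- s = 0.25: √(0.260 + 0.125) = √0.385 = 0.62; variance ratio 0.385/0.260 ≈ 1.5.
- s = 0.5: √(0.260 + 0.500) = √0.760 = 0.87; variance ratio 0.760/0.260 ≈ 2.9.

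If each participant's shift is the same in both sessions, this term vanishes.

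**5. Group comparison.** If a cigarette adds n to the change score and the proportions smoking are p1 (PAIN) and p0 (NO PAIN), a comparison within one session is moved by (p1 − p0) × n. A between-group comparison of naloxone-minus-placebo differences is not moved by it.

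**The case against.** The strongest reply is that each participant is their own control. Section 14.2 uses the 15-minute measures to check for withdrawal relative to placebo, and section 14.4 summarises safety by study medication, so a placebo column always stands beside the naloxone column. This stands. A reader might infer that the plan understates naloxone-induced pupil dilation or mixes nicotine into the naloxone effect. For the comparison with placebo, the documents do not support that.

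A reader might also infer that a two-hour gap is planned. It is not. No section says that a session starts at methadone dosing, and the questionnaires and end-of-session care could take up part of the four hours. The list in section 10.2 is not strictly chronological either: the discounting task at 30 minutes is listed after a series that runs to two hours. In addition, the start-of-session wording in section 9.1.5 covers blood pressure, pulse and respirations, not pupil. These points leave the baseline time undefined; they do not supply one.

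Matching on daily cigarette consumption, with covariate adjustment if the groups differ significantly (section 14.2), reduces the smoking concern. It does not remove it, and section 14.2 itself concedes that its method is inferior to formal matching.

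Finally, a baseline taken soon after a cigarette carries some acute nicotine effect, and its decay would then appear as change in the opposite direction. That is a real cost of moving the baseline, but it applies equally in both sessions.

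**Conclusion.** The point holds as a minor weakness of precision and interpretation. The baseline time relative to injection is unspecified, the listed order puts the cigarette after it, and the statements on session timing conflict. The expected naloxone-minus-placebo difference is unbiased, given random order, effective blinding and the same procedures in both sessions.

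Only the pupil endpoint and the vital-sign safety summary are touched. The primary endpoint (discounting rate k) and peak COWS, SOWS and drug-effect VAS scores are not defined as changes from baseline. The missing baseline VASs are thus an inconsistency with no effect on their endpoint.

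The variance increase of about 1.5 to 2.9 times depends on the assumed shift SDs of 0.25 and 0.5 and on independent variation between sessions. The documents give neither the size nor the direction of any nicotine or methadone effect on pupil or vital signs, so no bias in beats per minute or millimetres can be claimed from them.

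**What to change.** - In section 10.2, take the baseline after the cigarette step, as the last step before injection, at the same stated time relative to injection in both sessions. Leave the cigarette and methadone timing unchanged.
- Align section 9.1.5 with that time. Its five-minute rest fits within the existing 20-minute interval.
- Add the subjective drug-effect VASs to the baseline list so that it matches section 9.5.
- Reconcile the session length and injection position in the synopsis with sections 4.1, 8.4.3, 9.1.5 and 10.2, and reconcile who smokes between sections 8.4.3 and 10.2. This point takes no position on which statement is right.

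The cost is a few lines of text. Apart from the baseline VAS ratings that section 9.5 already calls for, no measurement is added. This is a cheap improvement.

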11 ADVERSE EXPERIENCE REPORTING AND DOCUMENTATION

11.1 Adverse Events

An adverse event (AE) is any untoward medical occurrence in a clinical investigation of a patient administered a pharmaceutical product and that does not necessarily have a causal relationship with the treatment. An AE is therefore any unfavorable and unintended sign (including an abnormal laboratory finding), symptom or disease temporally associated with the administration of an investigational product, whether or not related to that investigational product. An unexpected AE is one of a type not identified in nature, severity, or frequency in the current Investigator's Brochure or of greater severity or frequency than expected based on the information in the Investigator's Brochure.

The Investigator will probe, via discussion with the subject, for the occurrence of AEs during each subject visit and record the information in the site's source documents. Adverse events will be recorded in the patient CRF. Adverse events will be described by duration (start and stop dates and times), severity, outcome, treatment and relation to study drug, or if unrelated, the cause.

AE Severity

The National Cancer Institute's Common Terminology Criteria for Adverse Events (CTCAE) Version 3.0 should be used to assess and grade AE severity, including laboratory abnormalities judged to be clinically significant. The modified criteria can be found in the study manual. If the experience is not covered in the modified criteria, the guidelines shown in Table 1 below should be used to grade severity. It should be pointed out that the term "severe" is a measure of intensity and that a severe AE is not necessarily serious.

Version #: 1.9 Version Date: 12/09/2020 Page 21 of 37

Table 1. AE Severity Grading

| Severity (Toxicity Grade) | Description |
|---------------------------|---|
| Mild (1) | Transient or mild discomfort; no limitation in activity; no medical intervention or therapy required. The subject may be aware of the sign or symptom but tolerates it reasonably well. |
| Moderate (2) | Mild to moderate limitation in activity, no or minimal medical intervention/therapy required. |
| Severe (3) | Marked limitation in activity, medical intervention/therapy required, hospitalizations possible. |
| Life-threatening (4) | The subject is at risk of death due to the adverse experience as it occurred. This does not refer to an experience that hypothetically might have caused death if it were more severe. |

AE Relationship to Study Drug

The relationship of an AE to the study drug should be assessed using the following the guidelines in Table 2.

Table 2. AE Relationship to Study Drug

| Relationship to Drug | Comment |
|-------------------------|---|
| Definitely | Previously known toxicity of agent; or an event that follows a reasonable temporal sequence from administration of the drug; that follows a known or expected response pattern to the suspected drug; that is confirmed by stopping or reducing the dosage of the drug; and that is not explained by any other reasonable hypothesis. |
| Probably | An event that follows a reasonable temporal sequence from administration of the drug; that follows a known or expected response pattern to the suspected drug; that is confirmed by stopping or reducing the dosage of the drug; and that is unlikely to be explained by the known characteristics of the subject's clinical state or by other interventions. |
| Possibly | An event that follows a reasonable temporal sequence from administration of the drug; that follows a known or expected response pattern to that suspected drug; but that could readily have been produced by a number of other factors. |
| Unrelated | An event that can be determined with certainty to have no relationship to the study drug. |

11.2 Serious Adverse Experiences (SAE)

An SAE is defined as any AE occurring at any dose that results in any of the following outcomes:

- death
- a life-threatening adverse experience
- inpatient hospitalization or prolongation of existing hospitalization
- a persistent or significant disability/incapacity

Version #: 1.9 Version Date: 12/09/2020 Page 22 of 37

a congenital anomaly/birth defect

Other important medical events may also be considered an SAE when, based on appropriate medical judgment, they jeopardize the subject or require intervention to prevent one of the outcomes listed.

11.2.1 Serious Adverse Experience Reporting

Study sites will document all SAEs that occur (whether or not related to study drug) per UCSF CHR Guidelines. The collection period for all SAEs will begin after informed consent is obtained and end after procedures for the final study visit have been completed.

In accordance with the standard operating procedures and policies of the local Institutional Review Board (IRB)/Independent Ethics Committee (IEC), the site investigator will report SAEs to the IRB/IEC.

12 DISCONTINUATION AND REPLACEMENT OF SUBJECTS

12.1 Withdrawal of Subjects

A subject may be discontinued from study treatment at any time if the subject or the investigator feels that it is not in the subject's best interest to continue. The following is a list of possible reasons for study treatment discontinuation:

- Subject withdrawal of consent
- Subject is not compliant with study procedures
- Adverse event that in the opinion of the investigator would be in the best interest of the subject to discontinue study treatment
- Recurrent intoxication or + UDS
- Lost to follow-up
- Positive pregnancy test (females)
- Change in methadone dose between Sessions 1 & 2
- +COVID-19 test or inability to enter Ward 95 due to screening positive for COVID-19 symptoms/recent exposure

If a subject is withdrawn from treatment due to an adverse event, the subject will be followed by the Investigator until the abnormal parameter or symptom has resolved or stabilized.

Version #: 1.9 Version Date: 12/09/2020 Page 23 of 37

All subjects are free to withdraw from participation at any time, for any reason, specified or unspecified, and without prejudice.

Reasonable attempts will be made by the investigator to provide a reason for subject withdrawals. The reason for the subject's withdrawal from the study will be specified in the subject's source documents.

